#### 12.2.4. Severity of Adverse Event

The Investigator will make an assessment of the severity of each AE and SAE according to the National Cancer Institute (NCI) Common Terminology Criteria for Adverse Events (CTCAE), v. 5.0, 2017.

For terms not specified in the CTCAE, the criteria in [Table 6](#) should be used to determine the grade severity.

**Table 6: Criteria for Determining the Grade/Severity of Adverse Event Terms Not Specified by the NCI CTCAE Criteria**

Grade	Criteria
1	Mild; asymptomatic or mild symptoms, clinical or diagnostic observations only; intervention not indicated
2	Moderate; minimal, local, or noninvasive intervention indicated; limiting age-appropriate instrumental activities of daily living a
3	Severe or medically significant but not immediately life-threatening; hospitalization or prolongation of hospitalization indicated; disabling; limiting self-care activities of daily living b
4	Life threatening consequences; urgent intervention indicated
5	Death related to adverse event

CTCAE = Common Terminology Criteria for Adverse Events.

a Instrumental activities of daily living refer to preparing meals, shopping for groceries or clothes, using the telephone, managing money, etc.

b Self-care activities of daily living refer to bathing, dressing and undressing, feeding self, using the toilet, taking medications, and not bedridden.

#### 12.3. Pregnancy

Should a pregnancy occur, it must be reported and recorded on Fibrocell's pregnancy form. Pregnancy in itself is not regarded as an AE unless there is a suspicion that an IP may have interfered with the effectiveness of a contraceptive medication.

The outcome of all pregnancies (spontaneous miscarriage, elective termination, normal birth or congenital abnormality) must be followed up and documented even if the subject was discontinued from the study.

All reports of congenital abnormalities/birth defects are SAEs. Spontaneous miscarriages should also be reported and handled as SAEs. Elective abortions without complications should not be handled as AEs.

## **13. STATISTICS**

Pre-designed CRFs will be used to collect data for analyses. A clinical database will be managed by a sponsor's representative for this study. The database will be constructed based on the CRF data entry plus laboratory data information. Data queries will be generated and resolved. In addition, range checks of the CRF fields, plausibility and consistency checks across CRF pages will be performed to assess consistency, accuracy and completeness of the data collected and entered into the CRF. Standard SAS datasets will be generated and provided for analysis.

### **13.1. Sample Size Determination**

Since this is primarily a safety study, no formal sample size determination is or was made.

### **13.2. Analysis Populations**

#### **Full Analysis Set**

The primary population for analysis of efficacy is the full analysis set (FAS). The FAS population includes subjects who were administered FCX-013.

#### **Per-Protocol**

The per-protocol (PP) population is defined as all subjects in the FAS who complete the Week 12 assessments within the specified visit windows, and who do not meet any of the following criteria:

- Did not receive intradermal injections of FCX-013 in the treated lesion(s);
- Did not receive at least 10 doses of veledimex within 15 days of administration of FCX-013;
- Other significant protocol violations, including medically significant violations of inclusion/exclusion criteria or prohibited medications/treatments which may reasonably affect clinical assessments.

#### **Safety**

The safety population includes subjects who were administered FCX-013.

### **13.3. Demographic and Baseline Characteristics**

The descriptive summaries of subjects' demographic and baseline characteristics will be presented. A detailed description of subject disposition will be provided.

Subject characteristics will include a summary of the following:

Subject demographics.

Baseline disease characteristics as determined at screening. Pre-existing medical conditions.

Continuous variables will be summarized using number of observations, mean and standard deviation, median and minimum and maximum values. Categorical values will be summarized using number of observations and percentages.

### **13.4. Safety Analyses**

Subject demographics and relevant baseline data will be listed and described. Inclusion and exclusion criteria ensure that participants are suitable for the study. Premature termination will be described.

Physical examinations, vital signs, ECG data, concomitant medications, and laboratory results, including RCL analyses will be listed, and relevant changes will be described by subject and overall, as applicable.

Adverse events will be coded using the Medical Dictionary for Regulatory Activities (MedDRA) AE dictionary. Adverse events will be grouped into pre-treatment AEs and TEAEs and will be described by preferred terminology and by body system. The number of adverse event entries, as well as the number of subjects will be described, including by AE type, relationship to FCX-013 plus veledimex, seriousness, and severity of AEs.

### **13.5. Efficacy Analyses**

All subjects who were administered FCX-013 and had at least one assessment of the target lesion post-administration will be included in the efficacy population.

The change from baseline in the LoSCAT and durometry scores (average score at each applicable timepoint) will be reported descriptively, as will changes in the SkinDex 29+3 scores. The primary method of handling data will be last observation carried forward (LOCF).

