## **7. INVESTIGATIONAL PLAN**

### **7.1. Overall Study Design**

This is an open-label, single arm Phase 1/2 study being conducted by Fibrocell to evaluate FCX-013 in subjects with moderate to severe localized scleroderma/morphea. Approximately ten subjects will be enrolled and receive FCX-013.

The study is divided into the following periods: Screening (including Manufacture), Treatment, and Long-Term Follow-Up. The Screening Period consists of entry criteria evaluations, the collection of one set of three 3-4 mm biopsies for the manufacture of FCX-013 product, and the identification of potential target sclerotic lesions. Due to the FCX-013 manufacturing process, the Screening Period is expected to have a duration of approximately 4-6 months; however, this period can be extended to accommodate subject scheduling, variations in manufacturing duration and protocol mandated delays (i.e. pauses due to staggered treatment).

After FCX-013 manufacturing is complete, Fibrocell (the Sponsor) and the Investigator will mutually agree on the planned date for injection of FCX-013.

The Treatment Period will have a 12-week duration. One administration of FCX-013 will consist of a maximum of 4 mL of FCX-013 administered in up to sixteen (16) 0.25 mL intradermal injections. On Day 1, FCX-013 will be intradermally injected, using a retro-tracing technique, into the sclerotic lesion targeted for treatment. On Day 1, following the injection of FCX-013, subjects will initiate a 14-day course of veledimex to be taken orally daily. During the Treatment Period, subjects will be evaluated at Weeks 2, 4, and 12, and have an end-of-treatment visit at Week 12.

Treatment with FCX-013 will be staggered for the first three subjects. Administering FCX-013 following each of the first three subjects requires that the previous subject complete Week 4 evaluations, and that the Investigator(s) must have received approval from the Data Safety Monitoring Board (DSMB).

Safety and clinical efficacy evaluations are conducted throughout the study. Safety will be assessed through adverse events (AEs), physical examinations, vital signs, clinical laboratory evaluations, ECGs and concomitant medications.

The Long-Term Follow-Up period is an approximately 15-year period following End of Treatment in which an examination of injection sites is conducted, and safety is monitored annually, at a minimum.

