#### **7.5.2. Early Cessation of Study Treatment for an Individual**

Subjects may voluntarily stop receiving treatment at any time.

Unless a subject withdraws consent, subjects who voluntarily cease to receive treatment will continue to be followed as per the trial protocol and clinical assessment schedule to ensure that full data are obtained.

The Primary Investigator and/or the Sponsor may decide that early cessation of treatment is warranted for any one of the following reasons:

- Occurrence of AEs that pose a risk to safe participation
- Abnormal laboratory value(s) that pose a risk to safe participation
- Abnormal test procedure result(s) that pose a risk to safe participation
- Unsatisfactory therapeutic effect
- Condition no longer requires treatment
- Pregnancy

Subjects can withdraw from the study for any reason including worsening disease and to receive rescue therapy/standard-of-care treatment for worsening disease.

For subjects who are lost to follow-up, the Investigator should show due diligence by documenting in the source documents the steps taken to contact the subject (e.g., dates of telephone calls, emails).

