### **8.3. Subject Withdrawal Criteria**

A subject is free to withdraw from the study at any time for any reason without prejudice to their future medical care by the physician or at the institution. The Investigator or Sponsor may also withdraw the subject at any time in the interest of subject safety or for other reasons. Criteria for withdrawal include:

- Consent is withdrawn
- The subject refuses treatment and/or procedures/observations
- Occurrence of unmanageable AEs, or pregnancy
- For other reasons (e.g., significant protocol violation, non-compliance)

The Sponsor may be contacted if clarification is required.

The primary reason for withdrawal must be recorded on the case report form (CRF). Comments or complaints regarding the withdrawal made by the subject must also be recorded on the CRF. Withdrawal information will be communicated to the DSMB at each meeting. Withdrawal should be discussed with the medical monitor prior to withdrawal when possible. Subjects who wish to discontinue treatment or study procedures after receipt of FCX-013 will be asked to continue in the Long-Term Follow-Up Period.

Subjects who withdraw prior to FCX-013 administration will be considered a screen failure and will be replaced. The Sponsor reserves the right to terminate the study.

Discontinuation of FCX-013 administration does not mean discontinuation from the study. The study assessments and procedures for the visit and subsequent visits should be completed as indicated in the Schedule of Events ([Table 4](#)) and reason for discontinuation of FCX-013 administration should be documented in the subject's source documents and CRF.

If a subject discontinues from the study, every effort must be made to perform the study assessments and procedures specified for an Early Termination Visit (Week 12). The primary

reason for subject's withdrawal from the study should be documented in the subject's source documents and CRF.

Subjects who discontinue from the study following IP administration will be asked to participate in the Long-Term Safety Follow-up period.

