**Table 4: Schedule of Events**

Assessment ↓	Visit →	Screening	Baseline (Day 1)	Week 2 (Day 15, - 1/+3 days)	Week 4 (Day 29, ±5 days)	Week 12/ End of Treatment (Day 85, ±5days)	Week 26 (Month 6, ±4 weeks) Week 52 (Year 1, ±4 weeks)	Years 2-15* (52-week intervals, ±8 weeks)
Informed Consent		X						
Eligibility Criteria		X	X					
Demographics		X						
Medical/Surgical History		X	X					
Physical Exam/Vital Signs		X	X*	X	X	X		
Skin Assessments		X	X	X	X	X	X	
Electrocardiogram		X	X	X	X	X		
LoSCAT		X	X		X	X	X	
Durometry			X		X	X	X	
SkinDex			X			X	X	
(3) 3-4 mm biopsies/FCX-013		X						
Inject FCX-013			X					
Dispense/Collect Veledimex			X	X				
Prior/Concomitant Medications		X	X	X	X	X	X 	X 
Adverse Events		X	X	X	X	X	X 	X 
Hematology and Chemistry		X	X	X	X	X		
HIV, Hep B, Hep C Testing		X						
Urine Pregnancy Test, if applicable			X	X	X	X		
RCL Assay		X				X	X	X 

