### **13.7. Handling of Missing and Incomplete Data**

For efficacy evaluation, the treatment endpoint will be defined as one assessment time point, which includes the last measurement obtained during the study for a variable. No other imputation of values for missing data will be performed. Standard clinical monitoring and data management practices will be used to ensure the integrity of data.

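### LOCF as the primary efficacy method lets a Week 4 reading stand in for Week 12, 26 or 52, and Sections 13.5 and 13.7 define the efficacy result differently

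*Protocol*

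**What the plan says.** The protocol fixes the handling of missing efficacy data itself. Section 13.5 says "The primary method of handling data will be last observation carried forward (LOCF"), and the Synopsis repeats it. This governs the descriptive summaries of change from baseline in LoSCAT, durometry and SkinDex 29+3, which 13.5 reports by timepoint.

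Section 13.7 describes the result differently: "the treatment endpoint will be defined as one assessment time point, which includes the last measurement obtained during the study for a variable". It adds: "No other imputation of values for missing data will be performed".

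The entry bar is low. Under 13.5, subjects who received FCX-013 and "had at least one assessment of the target lesion post-administration will be included in the efficacy population", so a Week 4 reading alone is enough.

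On timing, Section 7.1 says that on Day 1 "subjects will initiate a 14-day course of veledimex to be taken orally daily". In Table 4 durometry and LoSCAT are done at Baseline, Weeks 4 and 12, and Weeks 26 and 52, not at Week 2. The first scheduled post-dose reading is therefore "Week 4 (Day 29, ±5 days").

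On leaving the study, Section 7.5.2 allows withdrawal for any reason, including "to receive rescue therapy/standard-of-care treatment for worsening disease".

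**The concern.** LOCF assumes that nothing changes after a subject's last reading. In this trial the inducing drug stops after two weeks, and the later visits are where one would learn whether any softening persists. A value taken shortly after the course and shown as a Week 12, 26 or 52 result puts an assumption in place of that information. A table of means does not reveal which values were carried. Because subjects may leave on account of worsening, the carried value may also predate the event that made them leave.

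The mismatch between 13.5 and 13.7 adds to this. If the endpoint is simply the last measurement, one subject's Day 29 value and another's Week 52 value are averaged as if taken at the same time. At stake is what the trial reports about durability, in a small first look at efficacy.

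**Working it through.** The protocol gives no sample size calculation, dropout rate or expected change, so there is no figure of its own to reproduce. The check has four parts.

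**1. Timing** (Section 7.1, Table 4). The last of 14 daily doses falls on Day 14.

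- Week 4: 29 − 14 = 15 days after the last dose; window Day 24 to 34 gives 10 to 20 days.
- Week 12: 85 − 14 = 71 days after; window Day 80 to 90 gives 66 to 76 days.
- A carried Week 4 value spans (85 − 29)/7 = 8 weeks to Week 12, 26 − 4 = 22 weeks to Week 26, and 52 − 4 = 48 weeks to Week 52.

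**2. Error from carrying forward.** With k of n subjects carried from Week 4:

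LOCF error = (k/n) × (mean Week 4 change in those k subjects − their true mean change at the later visit).

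With n = 10 (Section 7.2), each carried subject has weight 1/10 = 10%.

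Suppose leavers and stayers behave alike. Let D be the Week 4 softening and r the share of D truly present later. The truth is rD, and LOCF reports D × [k/n + (1 − k/n) × r]. All values of k and r are assumptions. As a percentage of D:

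| True share r | Truth | LOCF, k = 1 | LOCF, k = 2 | LOCF, k = 3 |
|---|---|---|---|---|
| 0 | 0 | 10 | 20 | 30 |
| 0.5 | 50 | 55 | 60 | 65 |
| 1 | 100 | 100 | 100 | 100 |

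The sign can reverse. If an assumed durometer change grows from −2 at Week 4 to −6 later and 2 of 10 are carried, LOCF gives (8 × −6 + 2 × −2)/10 = −5.2 against a true −6.0, about 13% too small.

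**3. Leavers who differ from stayers** (assumed, 2 of 10 lost).

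- Leavers worsen to −0.5D and stayers hold 0.5D. Truth: (8 × 50 − 2 × 50)/10 = 30% of D. LOCF: (8 × 50 + 2 × 100)/10 = 60%. Observed values only: 50%.
- Leavers had no response at Week 4 and still have none; stayers are at −6. Truth: (8 × −6 + 2 × 0)/10 = −4.8. LOCF: −4.8. Observed values only: −6.

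So observed means are nearer the truth in the first case and LOCF is exact in the second.

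**4. How likely is any gap?** The chance that at least one of 10 is missing at a visit, if losses are independent, is 1 − (1 − q)^10. For assumed missing rates q of 5%, 10%, 20% and 30% this is 40%, 65%, 89% and 97%.

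**The two sections side by side.** Under 13.5 with LOCF, a subject lost after Week 4 fills the later columns with the Day 29 value. Under 13.7, that value enters a single endpoint together with Week 52 values from subjects who stayed. The substitution occurs either way; only the label on the result differs.

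**The case against.** The strongest case for leaving the text alone is that little depends on it. Efficacy is secondary and descriptive, with about 10 subjects and no test or success rule. Subjects who stop treatment are still followed unless they withdraw consent. A best-effort assessment is requested at discontinuation, disposition is to be described in detail, and the per-protocol set requires an in-window Week 12 assessment. Observed means can also mislead, as part 3 of the working shows. All of this stands, and it limits the weight of the point. It does not remove it: the full analysis set is the primary efficacy population, the per-protocol rule does not protect Weeks 26 and 52, and no observed-value display is named.

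Some stronger readings are tempting but not supported:

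- *That early-termination readings are counted as Week 12.* Section 8.3 asks for the assessments "specified for an Early Termination Visit (Week 12"), and Section 10.2.4 calls them the End of Treatment assessments. Both say which procedures to perform. Neither says in which column the reading is tabulated.
- *That for SkinDex only Baseline can be carried for a dropout before Week 12.* The Week 12 set in Table 4 includes SkinDex, so a subject who attends the early-termination visit has a post-dose value.
- *That LOCF must overstate durability because MMP-1 is made only while veledimex is taken.* Section 5.2 says veledimex activates the switch. It does not say how fast expression stops or how long softening lasts.
- *That natural resolution makes LOCF plainly wrong.* Section 5.1 calls the disease self-limited, but inclusion criteria 1 and 2 require lesions unresponsive to standard care and three months of inactive disease.

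**Conclusion.** The point holds for durometry and LoSCAT. As written, the plan lets a reading from about two weeks after the veledimex course represent a result 8 to 48 weeks later. Sections 13.5 and 13.7 also do not agree on whether the result is a series of visits or one last measurement.

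The firm part of the size is the timing and the 10% weight of each carried subject. The direction and amount of error rest on assumed changes and dropout. For example, an assumed fade from −8 to −2 with 2 of 10 lost gives (8 × −2 + 2 × −8)/10 = −3.2 against −2.0, or 60% too large. A reader should not take that as an estimate for this trial: other assumptions give 13% too small, or no error.

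Because the analysis is descriptive, the consequence is a possibly misstated account of persistence, with no effect on type I error or on the primary safety objective. The change is worth making, mainly because it is cheap, but the trial does not stand or fall on it.

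**What to change.** Amend the Synopsis, Section 13.5 and Section 13.7 together:

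- Make the main efficacy summary the observed change from baseline at each scheduled visit, with the number of subjects observed.
- Show every subject's profile over time, as a plot or listing, marked with the time of and reason for discontinuation.
- Keep LOCF, if wanted, only as a labelled sensitivity display.
- Reconcile 13.7 with 13.5 so that values from different visits are not pooled as one endpoint.

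The cost is wording, with no added visits, subjects or procedures. The downside should be stated in the text: n may fall below 10 at later visits, and observed means are themselves biased if subjects who leave differ from those who stay. With about 10 subjects, the individual profiles let a reader judge this directly, so they are a necessary part of the change.

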### **13.6. Interim Analysis**

There will be no formal interim analysis.

### **13.7. Handling of Missing and Incomplete Data**

For efficacy evaluation, the treatment endpoint will be defined as one assessment time point, which includes the last measurement obtained during the study for a variable. No other imputation of values for missing data will be performed. Standard clinical monitoring and data management practices will be used to ensure the integrity of data.

## **14. ETHICS AND GENERAL STUDY CONDUCT CONSIDERATIONS**

### **14.1. Ethical Conduct of the Study**

The Investigator will ensure that this study is conducted in accordance with the principles of the “Declaration of Helsinki” (as amended in Edinburgh, Tokyo, Venice, Hong Kong, and South Africa), ICH guidelines, or with the laws and regulations of the country in which the research is conducted, whichever affords the greater protection to the study subject. As this study is conducted under a US Investigational New Drug application (IND), the Investigator will ensure that the basic principles of “Good Clinical Practice,” as outlined in 21 Code of Federal Regulations (CFR) 312, subpart D, “Responsibilities of Sponsors and Investigators,” 21 CFR, part 50 and 21 CFR, part 56 are adhered to.

Since this is a “covered” clinical trial, the Investigator will ensure that 21 CFR, part 54 is adhered to. This requires that the PI and all Sub-Is must provide documentation of their financial interest or arrangements with the Sponsor, or proprietary interests in the IP being studied. This documentation must be provided before participation of the PI and any Sub-I. The PI and Sub-Is agree to promptly notify the Sponsor or its designee if any relevant changes occur during the course of the study and for 1 year following completion of the study. Study completion is defined as the date that the last subject has completed the protocol-defined activities.

### **14.2. Institutional Review Board**

This study will be conducted in full compliance with the United States (US) CFR for IRBs 21 CFR, part 56. Before enrollment of subjects into the study, this protocol and any material to be provided to or seen by the subject (e.g., subject information letters, informed consent/assent forms, descriptions of the study used to obtain informed consent/assent, advertising material) will be submitted to an appropriate IRB for review and approval. Approval from the IRB must be obtained before starting the study and should be documented in a letter to the Investigator specifying the protocol number, protocol version, protocol date, documents reviewed, and date on which the committee met and granted the approval. IRB approvals must be sent to the Sponsor or its designee before initiation of the study.

Any amendments or modifications made to the protocol or any accompanying material to be provided to the subject after receipt of IRB approval must also be submitted to the IRB for review and approval before implementation.

The Investigator, or designee, will be responsible for obtaining IRB approval/renewal throughout the duration of the study at the frequency specified by the IRB. Copies of the investigator’s reports and the IRB written continuance of approval must be sent to the Sponsor or its designee.

The Investigator, or designee, should notify the IRB of important deviations from the protocol and any SAEs occurring at the site or other SAE reports received from the Sponsor or its designee, in accordance with IRB procedures.

All correspondence with the IRB must be retained in the study regulatory files.

